#### 8.4.3 Analysis of the Secondary Efficacy Endpoints

The number of episodes of nausea and vomiting, as well as the grades of nausea and vomiting will be calculated and reported for each of the two formulations at each time point. The rates of grade 3 vomiting will be compared between the two formulations at each time point using Fisher's exact test.

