#### Randomization and Arm Assignment

Period 1	Minimum 42-day washout	Period 2
Arm A Single dose of 4x40 mg liquid-filled capsules, fasted (n = 6-7)		Arm B Single dose of 4x40 mg liquid-filled capsules, fasted (n = 6-7)

Abbreviated Title: Enzalutamide Formulation PK  
Version Date: 03.11.2020

Patients will be randomized on a 1:1 basis between arms A and B.

The randomization will be performed by the NCI Central Registration Office at the time of enrollment.

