## 3 STUDY IMPLEMENTATION

### 3.1 STUDY DESIGN

This is a randomized, open-label, single-dose, 2-way crossover, pilot bioavailability trial evaluating two oral formulations of enzalutamide. All men (n=12-14) enrolled in the trial will receive oral enzalutamide in two formulations: Treatment A will be the standard liquid-filled, soft gelatin capsule (reference) formulation; Treatment B will be the liquid formulation (test product). Subjects will be randomized in Period 1 to one of two sequences: AB or BA. Following a minimum 42-day washout period, subjects will be crossed over in Period 2 to receive the treatment that they did not receive in Period 1. Blood samples will be collected for pharmacokinetic analysis.

Subjects are admitted to the Clinical Center on Day 1 (for the first 24-hours of PK sampling) and will take a single 160mg dose of enzalutamide. They are to return to the Clinical Center on Day 3 for the 48h, on Day 8 for the 168h, and Day 42 for the post-dose blood draws. After an appropriate washout period (at least 42 days), subjects will be crossed over in Period 2 to receive the treatment that they did not receive in Period 1. Subjects will be re-admitted to the Clinical Center to receive the study drug and blood samples will be drawn as described above on Days 1, 3, 8, and 42. Drug Administration

*Abbreviated Title: Enzalutamide Formulation PK*  
*Version Date: 03.11.2020*

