### **8.2 SAMPLE SIZE DETERMINATION**

This study will be conducted as a two-period randomized crossover trial design. Patients will be randomized to initially receive the standard liquid filled soft gelatin formulation (Arm A) followed later by the liquid formulation, or the liquid formulation as the test product (Arm B)

Abbreviated Title: Enzalutamide Formulation PK  
Version Date: 03.11.2020

followed by the liquid filled soft gelatin formulation. A total of 12 evaluable patients will be randomized into the two arms. It has been identified that a decrease of approximately 30-40 ug\*h/mL in the AUC (less than a 20% decrease in the AUC for the test version vs. the standard formulation) would permit the two formulations to be considered bioequivalent, and it may be expected that the actual difference between the formulations may be a decline of approximately 10% (approximately 20 ug\*h/mL). When the sample size in each sequence arm is 6, (a total sample size of 12) a crossover design will have 80% power to reject the null hypothesis that the Arm B mean minus the Arm A mean is below -40 ug\*h/mL and the null hypothesis that the Arm B mean minus the Arm A mean is above 0 ug\*h/mL, i.e., that the two groups are not equivalent, in favor of the alternative hypothesis that the means of the two treatments are equivalent, assuming that the expected difference in means is -20 ug\*h/mL, the standard deviation of differences,  $s_d$ , is 20 ug\*h/mL, and that each test is made at the 5% level.

It is expected that approximately 1 patient per month may enroll onto this trial. Thus, to enroll 12 evaluable patients, it is anticipated that one year may be required. To allow for the possibility of a small number of patients who do not have full measurements obtained based on both drug administrations, the accrual ceiling will be set at 14 patients.

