### 8.3 POPULATIONS FOR ANALYSIS

Modified intention to treat. Only patients who participated in both drug administrations and have blood draws on at least 3 of the 4 required dates for each of the two administrations.

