#### 8.4.4 Safety Analyses

Toxicity data: tabulated counts. The primary toxicity, nausea and vomiting, will be reported per arm at each of the time points when the drugs are administered.

*Abbreviated Title: Enzalutamide Formulation PK*  
*Version Date: 03.11.2020*

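### The grade 3 vomiting comparison uses unpaired Fisher tests in a crossover; one within-man estimate over both periods would use the data better, though no test is powered at low rates

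*Combined protocol and SAP*

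**What the plan says.** Section 3.1 describes a two-period crossover in which "subjects will be crossed over in Period 2 to receive the treatment that they did not receive in Period 1". Section 2.3.1 states "Patients will be randomized on a 1:1 basis between arms A and B". Section 8.2 sets the size: "A total of 12 evaluable patients will be randomized into the two arms", and "the accrual ceiling will be set at 14 patients". Section 8.3 restricts the analysis population: "Only patients who participated in both drug administrations" count, with a further requirement on blood draws.

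For the primary AUC endpoint, Sections 8.4.1 and 8.4.2 name a non-parametric method written for two-period change-over data. For the secondary endpoint, Section 8.4.3 plans counts and grades of nausea and vomiting by formulation, plus one formal test: "The rates of grade 3 vomiting will be compared between the two formulations at each time point", with Fisher's exact test. Section 8.4.4 adds that nausea and vomiting, named as the primary toxicity, "will be reported per arm at each of the time points when the drugs are administered".

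For this test the plan gives no definition of time point, no alpha or sidedness, no expected rate, no power, and no rule for combining results across time points.

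**The concern.** The crossover makes each man his own control. The AUC analysis uses that; the vomiting analysis does not. Fisher's exact test treats the liquid and capsule columns as different men.

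This is the only formal comparison planned for the safety and tolerability objective. Section 9.5 says the liquid without its capsule has not been evaluated for safety and names local irritation as a possible added risk. If the test can hardly ever reach significance, a non-significant result may be taken as evidence that the two formulations are equally well tolerated. If the two administrations gave different answers, the plan would not say which one stands.

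**Working it through.** **The plan's own figure.** No power is stated for vomiting. The size of 12 comes from the AUC equivalence test in Section 8.2: limits -40 and 0, expected difference -20, SD of differences 20, each test at 5%. Two one-sided t-tests with SE = 20/√N and N-2 degrees of freedom give 78.4% power at 5 per sequence (N=10) and 88.4% at 6 per sequence (N=12). So 12 is the smallest balanced size that reaches 80%. It was chosen for AUC, not for vomiting.

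**Inputs for vomiting.** From the documents: 12 evaluable men, 1:1 allocation, hence about 6 v 6 in each period (about 7 v 7 at the ceiling of 14). Assumed, because the plan is silent: two-sided 0.05, capsule rate 5%, liquid rate 20% to 50%, and outcomes independent within a man.

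**Reading 1: one test per administration.** Within a period, the men on liquid and the men on capsule are different men. With x events on one side and none on the other, the two-sided Fisher p-value is 2 × C(6,x)/C(12,x):
- 4/6 v 0/6: 2 × 15/495 = 0.061
- 5/6 v 0/6: 2 × 6/792 = 0.015

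The only other significant pattern is 6/6 v 1/6 or more extreme (6/6 v 1/6: p=0.015). At 5% v 50%, power per test is 0.95⁶ × 7/64 + 6 × 0.05 × 0.95⁵ × 1/64 = 0.0804 + 0.0036 = 8.4%.

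**Reading 2: pooled over periods.** Each of the 12 men appears once under liquid and once under capsule, so the columns are not independent. Nominal 12 v 12 power, computed as if they were, is 4.1% at 5% v 20% and 16.4% at 5% v 30%. These figures exceed McNemar's, but they rest on the independence that repeated observations on the same men do not guarantee.

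**Within-man comparison.** Exact McNemar uses only men who vomit on one formulation and not the other. If all d discordant men point the same way, p = 2 × 0.5^d: d=5 gives 0.0625 and d=6 gives 0.031. The discordance probabilities are p_L(1-p_C) for liquid only and p_C(1-p_L) for capsule only; at 5% v 50% these are 0.475 and 0.025. Exact enumeration gives:

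| Capsule v liquid (assumed) | One 6 v 6 Fisher test | At least one of two Fisher tests | McNemar, 12 pairs | Mainland-Gart, 6 per sequence |
|---|---|---|---|---|
| 5% v 20% | 0.1% | 0.2% | 1.1% | 0.2% |
| 5% v 30% | 0.8% | 1.6% | 7.3% | 2.4% |
| 5% v 50% | 8.4% | 16.1% | 44.9% | 28.0% |

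The third column is 1-(1-power)² with no correction for testing twice. At 7 v 7 the per-test Fisher power is 0.3%, 2.1% and 17.5%; McNemar on 14 pairs gives 2.4%, 13.1% and 59.8%.

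**What an interval would show.** With no events in 12 men, the exact two-sided 95% upper limit for a single rate is 1-0.025^(1/12) = 26.5%. An interval states that uncertainty; a p-value of 1 does not.

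**The case against.** A reader might infer that the planned test is invalid or inflates the error rate. On the by-administration reading, which Section 8.4.4 supports, it does neither: each test compares different men, and its actual type I error is at most 0.3% for common rates up to 30%. Independence fails only on the pooled reading. The fault on the likelier reading is lost information and two uncombined answers.

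A reader might also infer that pairing would turn this into a powered comparison. If half the men vomited on liquid and none on capsule, McNemar would detect it with probability 61%, against 11% per Fisher test. That is one favourable assumption, plausible if at all for any vomiting, while the plan tests grade 3. The documents give no vomiting rate, and the reactions listed at 5% or more in Section 10.1.2.2 do not include vomiting. At 5% v 20%, McNemar's power is 1.1%. This objection stands.

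The thresholds also depend on assumptions. With a one-sided test at 0.05, 4/6 v 0/6 would suffice (15/495 = 0.030); at 7 v 7, 5/7 v 0/7 would suffice (two-sided p=0.021).

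Finally, this is a pilot sized for AUC, and tolerability is otherwise described through counts, grades and a questionnaire on the liquid. That limits the severity. It does not justify leaving an undefined term and an unpaired test when a paired summary needs no new data.

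**Conclusion.** The concern holds as one of efficiency and clarity. The formal tolerability comparison does not use the crossover pairing, and its time point is undefined. It yields either two valid but uncombined tests of about 6 v 6, or one pooled test whose independence assumption fails. With 12 men, two-sided 0.05 and outcomes independent within a man, McNemar has more power than either Fisher test, or both together, at each pair of rates in the table (44.9% against 8.4% per test at 5% v 50%).

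The gain at low grade 3 rates is a coherent paired estimate with an honest interval, not a test that can be relied on to detect a difference. Severity is minor to moderate: this is a secondary endpoint in a pilot, and the AUC conclusion does not depend on it.

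**What to change.** In Section 8.4.3:
- Define time point as the drug administration.
- Replace the Fisher tests with one within-man comparison over both periods. Tabulate, by sequence, men with the event on both formulations, liquid only, capsule only and neither, for grade 3 or higher and for any vomiting.
- Report the paired risk difference with an exact 95% CI.
- Label any exact McNemar or Mainland-Gart p-value descriptive, and state that a non-significant result does not show equal tolerability.
- Keep counts by period and formulation for all dosed men, including those who receive only one dose. The Section 8.3 restriction would drop a man who did not go on to his second dose, possibly because of the first.

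The cost is a few sentences and one table, with no new data. The choice of test has a price: McNemar does not adjust for a period effect, and the plan states 1:1 allocation without saying how balance is kept in 12 to 14 men. Mainland-Gart does adjust for period, with less power (28.0% against 44.9% at 5% v 50%). Tabulating by sequence lets the reader see any period effect whichever test is used.

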### 3.3 STUDY CALENDAR

Procedure	Screening	Baseline	Period 1					Period 2				
			Day 1	Day 2	Day 3	Day 8	Day 42	Day 1	Day 2	Day 3	Day 8	Day 42
Confirmation of diagnosis	X	X										
History and PE	X	X	X g				X	X d				X
Vital signs	X	X	X			X	X	X d				X
Performance Score	X	X					X	X d				X
Labs	X a	X b	X f				X	X d				X
Urinalysis	X	X					X	X d				X
ECG	X	X					X	X d				X
PK c	X	X	X	X	X	X	X	X	X	X	X	X
Adverse Events			X	X	X	X	X	X	X	X	X	X
Concomitant Medications			X			X	X	X d			X	X
Questionnaire			X e					X e				

aFor screening labs see Section 2.2

bFor baseline labs see Section 2.4;

cSee Section 5.1 for complete details.

dWith the exception of PK and adverse events, all assessments and labs on Period 2 Day 1 do not need to be repeated if within 8 days of Period 1 Day 42.

eSubjects will be given a questionnaire (see APPENDIX B) to complete following the administration of the liquid (test) formulation to assess the tolerability. The questionnaire is only completed on the day the liquid formulation is administered. It is not necessary to complete the questionnaire on the day the capsule formulation is administered.

fLabs do not need to be repeated if they were completed at screening/baseline within 17 days of of period 1 day 1.

gH&P may be performed within 17 days of treatment initiation.

*Abbreviated Title: Enzalutamide Formulation PK*  
*Version Date: 03.11.2020*

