### **6.3 TOXICITY CRITERIA**

The following adverse event management guidelines are intended to ensure the safety of each patient while on the study. The descriptions and grading scales found in the revised NCI Common Terminology Criteria for Adverse Events (CTCAE) version 5.0 will be utilized for AE reporting. All appropriate treatment areas should have access to a copy of the CTCAE version 5.0. A copy of the CTCAE version 5.0 can be downloaded from the CTEP web site ([http://ctep.cancer.gov/protocolDevelopment/electronic\\_applications/ctc.htm](http://ctep.cancer.gov/protocolDevelopment/electronic_applications/ctc.htm)).

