#### **Secondary efficacy endpoints:**

To evaluate the safety and tolerability of two oral formulations of enzalutamide following a single 160 mg dose in male subjects with prostate cancer.

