#### 10.1.2.2 Other adverse events

The most common adverse drug reactions ( $\geq 5\%$ ) reported in patients receiving enzalutamide in the randomized clinical trial were asthenia/fatigue, back pain, diarrhea, arthralgia, hot flush, peripheral edema, musculoskeletal pain, headache, upper respiratory infection, muscular weakness, dizziness, insomnia, lower respiratory infection, spinal cord compression and cauda equina syndrome, hematuria, paresthesia, anxiety, and hypertension. Grade 3 and higher adverse reactions were reported among 47% of enzalutamide-treated patients and 53% of placebo-treated patients. Discontinuations due to adverse events were reported for 16% of enzalutamide-treated patients and 18% of placebo-treated patients. The most common adverse reaction leading to treatment discontinuation was seizure, which occurred in 0.9% of the enzalutamide-treated patients compared to none (0%) of the placebo-treated patients. Hypertension was also seen in patients who received enzalutamide relative to placebo (6.6% vs. 3.3%).

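### The only significance test for tolerability is grade 3 vomiting, which 12 men can hardly ever make significant; lower-grade vomiting and all nausea are reported but not tested

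*Combined protocol and SAP*

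**What the plan says.** The secondary objective (1.1.2, repeated in 8.1) is "To evaluate the safety and tolerability of two oral formulations of enzalutamide following a single 160 mg dose in male subjects with prostate cancer". Section 6.3 says the "Common Terminology Criteria for Adverse Events (CTCAE) version 5.0 will be utilized for AE reporting", so each event carries an ordinal grade.

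Section 8.4.3 first describes: "The number of episodes of nausea and vomiting, as well as the grades of nausea and vomiting will be calculated and reported" for each formulation at each time point. It then plans one test: "The rates of grade 3 vomiting will be compared between the two formulations at each time point using Fisher's exact test". No significance level, expected rate or reason for the cut is given. Section 8.4.4 adds tabulated counts and states: "The primary toxicity, nausea and vomiting, will be reported per arm at each of the time points when the drugs are administered".

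The Appendix B questionnaire offers no second comparison. The footnote in 3.3 says: "The questionnaire is only completed on the day the liquid formulation is administered".

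Section 8.2 fixes the size: "A total of 12 evaluable patients will be randomized into the two arms". Each man takes both formulations.

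**The concern.** The test does not match the toxicity that the plan puts first. Nausea is not tested at all, and vomiting is tested only at the grade least likely to occur. Section 10.1.2.2 lists the reactions seen in at least 5% of men on daily treatment, and neither nausea nor vomiting is among them; here each man takes one dose of each formulation. Section 9.5 says the safety of the liquid without its shell is unevaluated, and 10.1.6 that nothing is known of its palatability. It is an inference, but a reasonable one, that any difference between formulations would lie mainly at grades 1 and 2.

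At stake is how the secondary objective is reported. A p-value near 1 from the one named test is easily read as evidence that the formulations are tolerated equally, when the test could hardly have given another result.

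The wording has a smaller defect. Grade 3 taken literally puts a man with worse vomiting among the non-events, whereas 10.1.2.2 itself summarises reactions as grade 3 and higher.

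**Working it through.** **The plan's own sizing figure.** The only one is for AUC (8.2): SD of differences 20, true difference -20, limits -40 and 0, two one-sided tests at 5%. With SE = 20/√12 = 5.77 and 10 degrees of freedom, simulated power is 88% at 12 men; at 10 men it is 78%. So 12 is the smallest balanced total that reaches 80%. Nothing in that calculation concerns tolerability.

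**Inputs for the tolerability test.** 12 men per formulation (8.2), or 6 per formulation if each period is tested separately. Two-sided 0.05 is assumed, since none is stated for this test.

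**What the planned test needs.** For k cases against 0 with n men per formulation, the two-sided Fisher p-value is 2 × C(n,k)/C(2n,k).

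- n = 12, k = 4: 2 × 495/10,626 = 0.093.
- n = 12, k = 5: 2 × 792/42,504 = 0.037.
- n = 6, k = 4: 2 × 15/495 = 0.061.
- n = 6, k = 5: 2 × 6/792 = 0.015.

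Either way at least 5 against 0 is required. With no grade 3 case on the capsule, power at 12 per formulation is P(at least 5 of 12): 0.4% at a true grade 3 rate of 10%, 7% at 20% and 28% at 30%. The chance of no grade 3 case in 12 liquid doses is (1 - p)^12: 89% at p = 1% and 54% at p = 5%.

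**Illustration of the cut.** Suppose 6 of 12 men vomit at grade 1-2 on the liquid and none on the capsule. The planned test compares 0/12 with 0/12, p = 1. Counting any grade, Fisher gives 2 × 924/134,596 = 0.014, and the exact McNemar test (6 against 0 discordant men) gives 2 × 0.5^6 = 0.031.

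**Power under assumed rates.** Assumptions: capsule 5% any grade; 30% of events grade 2, 5-20% grade 3, the rest grade 1; a man's two administrations independent. The liquid's grade 3 rate is its any-grade rate times 5-20%, for example 60% × 20% = 12%. Fisher power is exact: the binomial probabilities summed over all tables with p ≤ 0.05. The paired test is an exact signed-rank test on the full grade, by simulation.

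| Liquid, any grade | Liquid, grade 3 | Planned Fisher test, 12 v 12 | Paired exact rank test, 12 men |
|---|---|---|---|
| 30% | 1.5-6% | under 0.1% | about 8% |
| 40% | 2-8% | up to 0.1% | about 23% |
| 50% | 2.5-10% | up to 0.4% | about 45% |
| 60% | 3-12% | up to 0.8% | about 67% |

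At 50% against 5%, an any-grade exact McNemar test also gives 45%. The gain therefore comes mostly from counting grades 1 and 2, not from fine ranking of grades.

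**If the comparison is made period by period.** An unpaired exact rank test on the full grade at 6 v 6 has about 1%, 3%, 9% and 19% power in the same four cases. Using both periods within each man is thus an essential part of the improvement.

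**The case against.** The strongest reply is that nothing is hidden. Episodes and grades of both nausea and vomiting must be reported by formulation, with counts per arm as well, so 6 of 12 against 0 of 12 would be plain in the tables. This is a pilot sized only for AUC, and testing severe events while describing milder ones is a defensible choice.

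The assumed rates can also be challenged. The liquid is the capsule's own fill (10.1.3.2), 9.5 names local irritation and aspiration as the added risks rather than vomiting, and 10.1.2.2 gives no reason to expect 30-60%. Paired power is low at the lower end of that range, and it falls further if the capsule rate is higher: at 50% against 20%, the any-grade McNemar test has 15%.

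Much of this stands. A reader might infer that a liquid sickening half the men at grade 1-2 would show no difference from the capsule. Sections 8.4.3 and 8.4.4 do not support that: only the p-value would miss it. Nor is grade 3 vomiting the only planned comparison of tolerability; it is the only significance test.

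What the reply does not answer is why the plan names a test that can almost never reject and leaves out half of its own primary toxicity.

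**Conclusion.** The point holds as a mismatch between the named test and the tolerability objective. That the test needs 5 against 0, and gives p = 1 when all events are grade 1-2, follows from the design and rests on no assumed rate. It is very unlikely to be significant unless grade 3 vomiting is itself common: even at a true rate of 20% against none, power is 7%.

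The comparison of under 1% with about 8-67% rests on assumed event rates, an assumed split of grades and independence within man. It shows the direction and rough size of the gain, not a forecast. Nor does it show that 12 men suffice for a tolerability conclusion under any test.

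The change is worth making because it is cheap and the present p-value invites misreading. The primary AUC analysis and data collection are unaffected.

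**What to change.** In 8.4.3, replace the grade 3 test with wording to this effect:

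- For each man and each administration, take the worst CTCAE grade of nausea and the worst CTCAE grade of vomiting, with 0 if none.
- Compare the formulations within man, over both periods, with a paired exact rank test on the full ordinal scale, separately for nausea and vomiting.
- Report the paired difference in any-grade rates with a confidence interval, and state that a non-significant result is not evidence of equal tolerability.
- Label these comparisons secondary.
- Tabulate grade 3 or higher vomiting by formulation, without a test.

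Men with only one administration cannot enter the paired comparison and should remain in the tables. The separate tests at each time point go; the descriptive reporting by time point stays.

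The cost is one paragraph of text, with no new data, visits or patients. The downside is that two secondary comparisons replace one.
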